6.1.2 PK Week

The PK week is defined as 7 days prior to C1D1 where a single dose of HMPL-306 will be administered on Day 1 of PK week (Day -7 relative to C1D1). Blood samples and ECG assessments will be collected at intervals as specified in [Appendix 1](#). These samples will be analyzed for plasma concentrations of HMPL-306, 2-HG, and other biological markers as defined by the sponsor. PK week is applicable to every cohort in the dose escalation part only. See [Appendix 1](#) for more details. PK week for a particular dose cohort will be considered optional and not mandatory if PK week data from 5 patients have been collected at the same dose.

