7.5.2 Dose Adjustment Outside the DLT Assessment Window (Including Dose Expansion Part)

Dose adjustments are to be made for any AE deemed at least possibly related to HMPL-306.

Dose adjustments are to be made as outlined in [Table 8](#) and [Table 9](#).

Table 8 Dose Adjustment for Hematologic Toxicity

CTCAE v5.0 Grade	Action
Grade 1 or 2	None
Grade 3 or 4 (believed to be related to HMPL-306 and NOT underlying disease)	
Hold drug.If the toxicity improves to Grade ≤ 2 within 7 days, then resume at original dose.If the toxicity recurs at original dose, then resume 1 dose level lower provided the toxicity improves to Grade ≤ 2 within 7 days.If the toxicity recurs in setting of prior dose level reduction, then resume 1 additional dose level lower provided the toxicity improves to Grade ≤ 2 within 7 days.In the event the toxicity does not improve to Grade ≤ 2 within 7 days or toxicity recurs despite 2 dose reductions, HMPL-306 treatment is to be permanently discontinued.

CTCAE=Common Terminology Criteria for Adverse Events.

Table 9 Dose Adjustment for Nonhematologic Toxicity

CTCAE v5.0 Grade	Action
Grade 1 or 2	None
Grade 3	
Hold drug.If the toxicity improves to Grade ≤ 2 within 7 days, then resume at original dose.If the toxicity recurs at original dose, then resume 1 dose level lower provided the toxicity improves to Grade ≤ 2 within 7 days.If the toxicity recurs in setting of prior dose level reduction, then resume 1 additional dose level lower provided the toxicity improves to Grade ≤ 2 within 7 days.In the event the toxicity does not improve to Grade ≤ 2 within 7 days or toxicity recurs despite 2 dose reductions, HMPL-306 treatment is to be permanently discontinued.
Grade 4	Permanently discontinue treatment with HMPL-306.

CTCAE=Common Terminology Criteria for Adverse Events.

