4.3. Exposure Endpoints

Duration of Exposure

Patients will receive dosing of HMPL-306 PO, QD, in each 28-day cycle. In dose escalation, dose will begin at **cci** mg QD of HMPL-306 in a 28-day continuous dosing treatment cycle. The dose will escalate successively according to the sequence of **cci** mg QD, **cci** mg QD and **cci** mg QD.

In dose expansion, HMPL-306 will be administered PO, QD, in a 28-day continuous dosing treatment cycle at MTD and/or RP2D.

The duration of exposure (months) = [Last non-zero dose date of study drug – first dose non-zero date of study drug (i.e. including single dose during the PK week) + 1] / 30.4375.

The actual duration of exposure (months) = [Cumulative days with non-zero study drug administered, and this includes the single dose during the PK week] / 30.4375.

Dose Intensity and Cumulative Dose

Algorithms for calculating parameters relevant to the dose exposure and intensity are included in [Table 9](#).

Table 9 Algorithms for Calculating Parameters Relevant to the Dose Exposure and Intensity

Parameter	HMPL-306 cc mg [§]
Dosing schedule per protocol	PO, QD, each day in a 28-day treatment cycle
Cumulative dose (mg)	Sum of the doses administered to a patient in the duration of exposure
Dose intensity (mg/day)	Cumulative dose (mg) / (duration of exposure*30.4375)
Relative dose intensity (RDI) (%)	100 * [Dose intensity (mg/day) / cc (mg/day)]
Percentage intended dose (PID) (%)	100 * [(actual duration of exposure) / (duration of exposure)]

[§] Different doses (e.g. ~~cc~~ mg PO QD, ~~cc~~ mg PO QD, etc.) of HMPL-306 may be evaluated. The calculation of relevant parameters will be adjusted accordingly based on the example presented in this table.

PO = *Per os* (oral administration); QD = *Quaque die* (once daily)

In addition, the RDI (%) will be categorized to the groups: < 50%; 50 - < 70%; 70 - < 90%; 90 - < 110%; \geq 110%.

Dose Interruptions, and Dose Reductions

- Dose interruption and dose reductions are all based on the dose administration data, the associated reasons for each of them include categories: (1) Adverse event, (2) DLT, and (3) Other.
- Dose modifications of study drug include dose interruption and dose reduction.

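### SAP Table 9 labels a days-dosed ratio as percentage intended dose: it ignores dose reductions and terminal holds, and it counts the planned PK-week gap as missed dosing

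*SAP*

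**What the plan says.** SAP 4.3 defines two durations. Duration of exposure is "Last non-zero dose date of study drug – first dose non-zero date of study drug", plus one day, in months. The second is given as "The actual duration of exposure (months) = [Cumulative days with non-zero study drug administered", with the PK-week dose counted. Both start from the PK-week dose where there is one.

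Table 9 then sets PID to "100 * [(actual duration of exposure) / (duration of exposure", times 100 as shown there. Cumulative dose is "Sum of the doses administered to a patient in the duration of exposure", dose intensity is "Cumulative dose (mg) / (duration of exposure*30.4375", and RDI divides dose intensity by the assigned daily dose. RDI is also reported in bands, among them 70 to <90% and 90 to <110%. SAP 5.2.10 summarises all of these on the safety analysis set.

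Three other places bear on this:

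- Protocol 6.1.2: in Part 1, "a single dose of HMPL-306 will be administered on Day 1 of PK week (Day -7 relative to C1D1". The PK week does not apply to Part 2. In Part 1 it becomes optional only once five patients at that dose have PK-week data.
- SAP 5.1.1, footnote to Table 13: one patient was enrolled in Part 2, and is pooled with Cohort 8.
- Protocol 7.5.1 and 7.5.2 (Tables 8 and 9): dosing is held for toxicity. It may resume, in some cases at a lower level. It stops for good if recovery does not come within 14 days (7.5.1) or 7 days (Tables 8 and 9). Recurrence also ends treatment; in the tables' words, "toxicity recurs despite 2 dose reductions, HMPL-306 treatment is to be permanently discontinued".

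**The concern.** The label promises dose received as a share of dose intended, but the formula delivers dosed days as a share of elapsed days up to the last dose. Three consequences follow.

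1. A day at a reduced dose counts the same as a day at full dose.
2. A hold that ends in permanent discontinuation falls after the last non-zero dose, so it is in neither the PID nor the RDI denominator. The patients whose toxicity did not recover are the ones whose final hold disappears.
3. The PK-week dose counts as one dosed day but brings seven calendar days with it, so six days on which no dose was planned are treated as missed.

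Exposure by dose level is part of how tolerability is described in this trial, and cohorts may be as small as three patients. One misdescribed patient is visible in a cohort summary of that size.

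**Working it through.** The plan states no PID value, so there is no figure to reproduce. I applied the Table 9 formulas to explicit dosing histories.

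**Inputs.** The formulas are from SAP 4.3 and Table 9; PK-week timing is from protocol 6.1.2; hold limits of 7 and 14 days are from protocol 7.5.1 and 7.5.2, used only as a range. The assigned dose is redacted but cancels from every ratio. A half-dose step is my assumption, because the dose steps are redacted too.

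**Formulas.** Let D be days with a non-zero dose, L = last dose day − first dose day + 1, M = total dose in units of the assigned daily dose, and P = planned dosing days to the stop (the PK-week dose day counts, the six dose-free days do not). The factor 30.4375 cancels.

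- PID (SAP) = 100 × D/L
- RDI (SAP) = 100 × M/L
- Share of intended dose to the stop = 100 × M/P

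**Perfect compliance with a PK week.** For n uninterrupted days from C1D1, D = n + 1 and L = n + 7, so PID = RDI = (n + 1)/(n + 7):

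- n = 14: 15/21 = 71.4%
- n = 28: 29/35 = 82.9%
- n = 56: 57/63 = 90.5%
- n = 168: 169/175 = 96.6%

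A perfectly compliant patient first reaches the 90 to <110% RDI band at n = 53, where 54/60 = 90%.

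**Terminal holds and reductions.**

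| History from C1D1 | PK week | PID (SAP) | RDI (SAP) | Share of intended dose to the stop |
|---|---|---|---|---|
| 28 days full | no | 28/28 = 100% | 100% | 28/28 = 100% |
| 28 days full | yes | 29/35 = 82.9% | 82.9% | 29/29 = 100% |
| 28 full, 7-day hold, stop | no | 28/28 = 100% | 100% | 28/35 = 80.0% |
| 28 full, 7-day hold, stop | yes | 29/35 = 82.9% | 82.9% | 29/36 = 80.6% |
| 28 full, 14-day hold, stop | no | 28/28 = 100% | 100% | 28/42 = 66.7% |
| 28 full, 14-day hold, stop | yes | 29/35 = 82.9% | 82.9% | 29/43 = 67.4% |
| 56 days full | yes | 57/63 = 90.5% | 90.5% | 57/57 = 100% |
| 28 full, 28 half | no | 56/56 = 100% | 42/56 = 75.0% | 42/56 = 75.0% |
| 28 full, 28 half | yes | 57/63 = 90.5% | 43/63 = 68.3% | 43/57 = 75.4% |
| 28 full, 7-day hold, 21 half | no | 49/56 = 87.5% | 38.5/56 = 68.8% | 38.5/56 = 68.8% |
| 28 full, 7-day hold, 21 half | yes | 50/63 = 79.4% | 39.5/63 = 62.7% | 39.5/57 = 69.3% |

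Within each PK-week setting, PID and RDI are the same for 28 clean days and for 28 days followed by either terminal hold. PID is also the same for 56 full-dose days and for 28 full plus 28 half-dose days. A hold followed by restart does lower PID, but only by the days missed and not by the mg shortfall afterwards.

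**The case against.** The other side has real points.

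- RDI is in mg, sits next to PID in Table 9, and is summarised by band, so reductions are not lost from the report.
- Interruptions and reductions are counted with reasons (SAP 5.2.10). TEAEs leading to interruption, reduction or discontinuation are tabulated (SAP 5.2.11.2), and so are reasons for stopping study drug (SAP 5.2.1). A patient held and then stopped for toxicity is therefore visible. These tables give patient counts and reasons, though, not dose lost, and no planned ratio captures a terminal hold.
- Measuring exposure to the last dose is a defined convention, and whether days on a required hold are intended dosing days is a choice. This is a good reason to leave RDI ending at the last dose. It does not justify the name percentage intended dose for a ratio with no dose in it.

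A reader might also infer four stronger things that the documents do not support.

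- *Reduced or terminally held patients score 100%.* This is true only without the PK-week dose. SAP 4.3 counts that dose, the PK week is the Part 1 default, and only one patient entered Part 2.
- *The bias is always upward.* The PK-week gap pulls PID and RDI down, including for fully compliant patients.
- *PID hides every trace of a reduction.* Protocol Tables 8 and 9 place reductions after a hold, and those hold days lower PID once dosing resumes. A direct step from full to half dose is an illustration, not the usual path in those tables.
- *The dose choice is distorted.* Protocol 4.1.1 bases the MTD on the mTPI-2 rule and the RP2D on the MTD, safety, PK and PD. PID is not a named input, and the exposure list in protocol 9.2.4 does not include it.

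**Conclusion.** The point holds. As written, PID does not measure what its label says. It cannot respond to the mg lost through a reduction, and neither PID nor RDI responds to a terminal hold. For a Part 1 patient with a PK week, 28 days followed by a 14-day hold and stop is reported as 82.9% when 67.4% of the dose intended to the stop was received (82.9% against 80.6% with a 7-day hold). Without a PK week it is 100% against 66.7% (or 80.0%). In the other direction, a fully compliant Part 1 patient at 28 days is reported at 82.9% instead of 100% on both PID and RDI, and falls in the 70 to <90% RDI band.

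These sizes rest on illustrative histories, an assumed half-dose step, and counting hold days before the stop as intended dosing days. How many patients followed each path is not in the documents. The effect is confined to a descriptive exposure summary: no hypothesis test, sample size or MTD decision depends on it. It should be corrected because a wrong value would appear under a plain label and the change is small.

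**What to change.** In SAP 4.3 and Table 9:

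1. Rename the present ratio percentage of days dosed.
2. Define PID = 100 × cumulative dose (mg) / [assigned dose (mg/day) × planned dosing days], with planned dosing days running from first dose to permanent discontinuation, death or data cut-off, whichever is earliest. Count the single PK-week dose day but not the six dose-free days that follow.
3. Exclude the same six days from the denominators of RDI and percentage of days dosed. Otherwise keep RDI to the last dose, with a footnote that it excludes terminal holds.
4. Name the date used for permanent discontinuation. Protocol 6.2.1.1 requires the reason for stopping to be recorded but does not mention a decision date, and the CRF is not among the documents. If no such date is captured, use the EOT date that SAP 5.1.2.5 already refers to, and say so. That section does not say whether this is the EOT visit. Protocol 6.1.18 sets the visit within 7 days (±3) of the last dose, so a visit date could cut a longer hold short or add a few days for a patient who stopped without one.

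The cost is SAP wording and one or two derivations. PID will look less favourable for patients with reductions or terminal holds, while PID and RDI will rise to 100% for fully compliant patients who had a PK week.

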4.4. Safety Endpoints

The safety analysis set is used to evaluate the safety variables including AEs, clinical laboratory data, vital signs, single 12-lead ECG parameters, echocardiogram (ECHO)/ multiple-gated acquisition (MUGA) parameters, physical examinations, ECOG performance status, and death. The safety data during the treatment period will be summarized, and the treatment period is defined as the duration from the date of the first study drug administration until 30+7 days (7-day window only applied to parameters collected by visit) after last dose or prior to the start of a subsequent anti-tumor therapy (whichever comes first).

4.4.1. Dose Limiting Toxicities (DLTs)

AEs will be assessed per the DLT criteria during the 28-day DLT assessment window in Cycle 1 for study Part 1, which starts with the first day of administration of study drug.

4.4.2. Adverse Events (AEs)

All AEs will be coded from verbatim text to preferred term (PTs) and grouped by system organ class (SOC) using the Medical Dictionary for Regulatory Activities (MedDRA) version 27.1 or higher. AEs will be collected from the time of signature of informed consent throughout the treatment period. AEs will be graded by investigator according to National Cancer Institute (NCI) Common Terminology Criteria for Adverse Events (CTCAE) v5.0. Missing severity grade will not be imputed, and will be summarized as 'Missing Grade' category in the by-grade analysis.

An AE is considered a TEAE:

(i) If one of the criteria is met:

- 1) If the onset date is on or after the start of study treatment until 30 days after the last dose or prior to the start of a subsequent anti-tumor therapy (whichever comes first), or if the onset date is missing; or
- 2) If the AE has an onset date before the start of study treatment, but worsened in severity after the study drug administration (i.e. SAE start date is on or after the start of study

treatment until 30 days after the last dose or prior to the start of a subsequent anti-tumor therapy (whichever comes first);

(ii) Beyond 30 days after the last dose or after the start of a subsequent anti-tumor therapy (whichever comes first), treatment-related SAEs will also be considered as TEAEs.

Investigator assessed AEs causality to study drug will be classified as "Related" and "Not Related". An AE with a missing causality will be classified as "Related" to study drug.

Other AE variables include treatment-related AEs, AEs of special interest (AESI), COVID-19 related AEs, AEs leading to study drug modifications (i.e. dose interruption, dose reduction, or study drug withdrawal), AEs leading to death, and SAEs. The AESI information will be identified programmatically by SMQ/PT.

For AEs which are not on-going, duration of AE (days) is defined as AE end date – AE start date +1; for on-going AEs, the end date will be listed as 'Ongoing'.

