8.2 Adverse Event Reporting

8.2.1 Adverse Event Reporting Period

After informed consent, but prior to initiation of study drug, all AEs and SAEs regardless of attribution will be collected. After initiation of study drug, all SAEs and AEs regardless of attribution will be collected until 30 days after the end of treatment or start of a new antitumor therapy, whichever is earlier. After this 30-day period, and if the patient has not started any other antitumor treatment, then investigators should report only SAEs that are considered to be related to the study drug until study discontinuation.

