8.6.3 Persistent or Recurrent Adverse Events

A persistent AE is one that extends continuously, without resolution between patient evaluation time points. Such events should only be recorded once in the CRF unless severity changes. If a persistent AE becomes more or less severe, it should be recorded again as a new CRF entry.

A recurrent AE is one that occurs and resolves between patient evaluation time points and subsequently recurs. All recurrent AEs should be recorded in the CRF as separate events, respectively.

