8.6.4 Abnormal Laboratory Values or Abnormal Vital Signs

Not every laboratory abnormality/abnormal vital sign qualifies as an AE. An abnormal laboratory test result/abnormal vital sign must be reported as an AE if it is a change from baseline and meets any of the following criteria:

- Is accompanied by clinical symptoms
- Results in a change in study treatment (eg, dosage modification, treatment interruption, or treatment discontinuation)
- Results in a medical intervention (eg, potassium supplementation for hypokalemia) or a change in concomitant therapy
- Is clinically significant by in the opinion of investigator

Investigators are responsible for reviewing all laboratory findings and abnormal vital signs and determining whether or not each abnormality should be reported as an AE.

If clinically significant laboratory abnormality is a sign of a disease or syndrome (eg, ALP and bilirubin 5 \times ULN associated with cholecystitis), only the diagnosis (eg, cholecystitis) needs to be recorded in the CRF.

If the clinically significant laboratory abnormality is not a sign of a disease or syndrome, that abnormality itself should be recorded as an AE or SAE in the CRF. If the laboratory abnormality can be characterized by a precise clinical term, that clinical term should be recorded as AE or SAE. For example, an elevated serum potassium level of 7.0 mmol/L should be recorded as “hyperkalemia.”

Observations of the same clinically significant laboratory abnormality from visit to visit should not be repeatedly recorded as AEs or SAEs in the CRF, unless their severity, seriousness, or etiology changes.

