9.2.4 Safety Analysis

The summary of the exposure to study treatment, AEs, AESIs, AEs leading to drug modification or discontinuation including DLTs, changes in laboratory results, and changes in vital signs, etc, will be presented. The severity of all AEs will be graded according to NCI CTCAE v5.0, and the AE verbatim term will be coded by the Medical Dictionary for Regulatory Activities (MedDRA).

TEAEs are defined as AEs that started or worsened in severity on or after the first dose of study treatment and no later than 30 days after the end of treatment.

Only those AEs that were treatment-emergent will be included in summary tables. All AEs, treatment-emergent or otherwise, will be presented in patient data listings. The number and frequency of patients experiencing adverse events will be summarized according to system organ class (SOC) and preferred terms. If a patient reports a TEAE more than once within that SOC/preferred term, the AE with the highest severity will be used in the corresponding severity summaries.

The following safety summaries will be produced:

- Overview of AEs
- Summary of DLTs (dose escalation part)
- Summary of TEAEs
- Summary of serious TEAEs
- Summary of AESIs
- Summary of TEAEs leading to dose interruption, dose reduction, or termination of treatment

The above summaries will be repeated for TEAEs related to study treatment.

Drug exposure including number of cycles received, total duration of exposure, cumulative dose received (mg), dose intensity, and relative dose intensity will be summarized. The number and percentage of patients requiring dose interruption, dose delay, dose reduction, and treatment discontinuation because of AEs will be summarized. Reasons for dose modifications will also be summarized.

For laboratory tests that are graded by NCI CTCAE v5.0 or higher, results will be summarized by grade. Treatment-emergent changes will be summarized by maximum post-baseline grade. A shift table summarizing the shift from baseline to maximum post-baseline grade will be presented.

The changes in vital signs and ECOG PS scores from baseline will be summarized. Changes in 12-lead ECG (for example, changes in QTcF) will be summarized.

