If a subject experienced the same adverse event (as identified by MedDRA preferred term) more than once during the study, the worst occurrence (e.g. worst grade) will be counted. Similarly, if a subject experienced more than one occurrence of the same SOC/PT, the worst occurrence (e.g. worst grade) will be counted within a particular SOC/PT. When summarizing AE by CTCAE grade, if a subject experienced more than one occurrence of the same SOC/PT, the worst severity grade will be counted. Each summary will be ordered by descending order of incidence of SOC and PT within each SOC. If the frequencies of SOC/PT tie, an alphabetic order of SOC/PT will be applied.

AESI Summary

AEs of special interest (AESI) are listed in the below table, and will be identified by MedDRA Query (SMQ)/PT:

AESI	Search Strategy
Abnormal hepatic function	Drug related hepatic disorders - comprehensive search (SMQ Code 20000006 Narrow search)
Differentiation syndrome	Differentiation syndrome (PT Code 10080638)

Abbreviations: AESI = adverse event of special interest; PT = preferred term; SMQ = standard MedDRA query.

All AESIs will be summarized in frequency and percentage by AESI category, PT and maximum CTCAE grade (All Grade, Grade ≥ 3 , Grade 1/2, Missing Grade). The following overall safety summary will also be summarized for each AESI category:

- AESI
- Treatment Related AESI
- AESI of CTCAE Grade 3 or higher
- AESI meeting SAE criteria
- AESI leading to dose modification
- AESI leading to dose reduction

- AESI leading to dose interruption
- AESI leading to dose discontinuation
- AESI leading to death

Moreover, time to AESI onset (days), AESI duration (days) and AESI outcome (the number and percent of patients) will be summarized descriptively.

Time to AESI onset is defined as the time interval from the date of first dose of study drug to the earliest onset date among all AESIs. That is, if a subject has multiple AESI occurrences, the earliest AESI onset date will be used as the onset date to calculate time to onset of AESI.

AESI duration (days) will only be calculated for ended AESI as (AE end date-AE start date+1).

Concomitant medication taken for hepatic function abnormal will be summarized by ATC and PT, and listed.

COVID-19 AE

COVID-19 AE will be identified by the following MedDRA Query (SMQ), and will be summarized (the number and percent of patients) by PT and maximum CTCAE grade (All Grade, Grade ≥ 3 , Grade 1/2, Missing Grade).

COVID-19	Search Strategy

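### SAP 4.4.2 has no rule for AE entries that are re-recorded when the grade changes, so its TEAE definition departs from the protocol whichever start date the new entry carries, and one AESI episode yields several durations

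*SAP*

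**What the plan says.** **Recording.** Protocol 8.6.3: "If a persistent AE becomes more or less severe, it should be recorded again as a new CRF entry". Protocol 8.6.4 applies the same idea to laboratory findings, which are not to be recorded repeatedly "unless their severity, seriousness, or etiology changes".

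**Collection before dosing.** Protocol 8.2.1: "After informed consent, but prior to initiation of study drug, all AEs and SAEs regardless of attribution will be collected".

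**Definition of a TEAE.** Protocol 9.2.4: "TEAEs are defined as AEs that started or worsened in severity on or after the first dose of study treatment". SAP 4.4.2 has two main limbs. Limb (i)1 reads "If the onset date is on or after the start of study treatment until 30 days after the last dose", cut short by any subsequent anti-tumor therapy; a missing onset date also qualifies. Limb (i)2 covers an AE with onset before treatment, "but worsened in severity after the study drug administration (i.e. SAE start date is on or after the start of study" treatment, within the same window. A separate provision adds treatment-related SAEs that occur later. SAP section 7, which lists changes from the protocol, mentions no change to the TEAE definition.

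**Counting and duration.** When a patient has the same event more than once, SAP 5.2.11.2 says "the worst occurrence (e.g. worst grade) will be counted". Time to AESI onset uses the earliest onset. For duration: "AESI duration (days) will only be calculated for ended AESI as (AE end date-AE start date+1". SAP 4.4.2 uses the same formula for AEs in general.

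**The concern.** Protocol 8.6.3 turns one continuing event into several records, and the SAP applies its rules record by record. Nothing in the SAP says that two entries belong to the same episode, and nothing compares the grade after first dose with the grade before it. The protocol's definition needs exactly that comparison, because it admits an event that began before dosing only if it got worse.

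TEAEs are a primary endpoint in both parts, and the non-efficacy tables are shown by dose level, where cohorts are small. A classification rule that depends on an unstated data-entry convention can change what those tables show. Durations of AESIs, differentiation syndrome among them, are also reported, and they are meaningful only per episode.

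**Working it through.** The plan gives no figure for this point, so the check is to apply the written rules to illustrative records. The dates below are assumed; the rules are the documents' own. Day 1 is first dose.

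**1. Pre-dose AE, two possible start dates for the new entry.**

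| Case | New entry starts on the date of the grade change | New entry keeps the original onset |
|---|---|---|
| Non-serious, improves: Grade 3 on Days -5 to 2, then Grade 2 on Days 3 to 9 | Second entry has onset Day 3, so (i)1 makes it a Grade 2 TEAE. Protocol 9.2.4: not a TEAE. **Conflict** | Onset Day -5, no worsening: not a TEAE. Agrees |
| Non-serious, worsens: Grade 1 before first dose, then Grade 2 after it | Second entry has a post-dose onset, so (i)1 makes it a TEAE. Agrees | Onset is pre-dose, so only (i)2 can apply. It is defined by an SAE start date, which a non-serious AE lacks: not a TEAE. Protocol 9.2.4: a TEAE. **Conflict** |

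Each convention gets one row right and the other wrong. Neither makes Protocol 8.6.3, Protocol 9.2.4 and SAP 4.4.2 consistent.

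**2. AE that starts after first dose.** Every entry within the window is treatment-emergent under either convention. The worst-occurrence rule then counts the patient once at the highest grade, and time to AESI onset takes the earliest date. Incidence, maximum grade and time to onset are therefore unaffected by the splitting.

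**3. Duration of such an AE.** Take a hepatic AESI at Grade 2, 3, 2 and 1 on Days 15–21, 22–28, 29–42 and 43–56. The formula is end − start + 1.

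- Whole episode: 56 − 15 + 1 = 42 days.
- New entries dated at the grade change: 21 − 15 + 1 = 7; 28 − 22 + 1 = 7; 42 − 29 + 1 = 14; 56 − 43 + 1 = 14. Mean (7 + 7 + 14 + 14)/4 = 10.5 days, median 10.5.
- New entries keeping the original onset: 21 − 15 + 1 = 7; 28 − 15 + 1 = 14; 42 − 15 + 1 = 28; 56 − 15 + 1 = 42.

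Either way one 42-day episode supplies four durations. If the last entry were still ongoing, the three closed entries would still enter the summary as ended AESIs.

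**4. Size of one misclassification.** One patient changes the incidence of a preferred term by 100/n percentage points. Protocol 4.1.1 sets cohorts of at least 3, extendable to 12; Part 1 is planned at 24 to 30 evaluable patients and the study at 40 to 50.

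- n = 3: 33.3 points; n = 6: 16.7; n = 12: 8.3
- n = 24 to 30: 4.2 to 3.3
- n = 40 to 50: 2.5 to 2.0

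**The case against.** The strongest reply is that the start date of a regraded entry is a data-entry matter, settled in the CRF or its completion guidelines, which are not part of these documents. Limb (i)2 suggests that some records do keep a pre-dose onset after a severity change. If so, improved AEs never become TEAEs. That is fair, and a reader should not infer that the SAP certainly counts improvement as emergence; the documents do not establish it. The reply does not rescue the rule, because under that convention the SAE start date parenthesis loses non-serious AEs that worsened.

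Second, the exposed group is narrow. Protocol 8.6.5 treats conditions present at screening as AEs only if they worsen, and inclusion criterion 7 requires recovery from clinically relevant effects of earlier cancer therapy. The Schedule of Events footnotes speak only of AEs due to protocol-required interventions being collected from consent, which may narrow it further. This stands: misclassification is limited to AEs that arise between consent and first dose and change grade afterwards, in a patient with no other qualifying record of that term.

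Third, a reader might infer that splitting inflates TEAE incidence generally. It does not; the worst-occurrence rule protects incidence and maximum grade for events that begin on treatment.

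Fourth, the study is single-arm and descriptive, and all AEs are listed with dates and grades, so a careful reader could reconstruct episodes. That limits the harm but does not correct the summary tables.

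**Conclusion.** Wrong as written. The SAP's TEAE rule does not implement the protocol's definition under either start-date convention, and SAP section 7 does not declare a change. The direction of the error depends on the convention: over-counting of improved pre-dose AEs if the new entry carries the change date, under-counting of worsened non-serious pre-dose AEs if it keeps the original onset. The second conclusion takes the SAE parenthesis as the operative test of worsening, as its wording indicates.

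For AEs that start after first dose, the only error is in AE and AESI duration, and it arises under both conventions.

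The number of affected patients cannot be derived. The range of 33 points (cohort of 3) to 8 points (cohort of 12), and 2 to 2.5 points over 40 to 50 patients, is the effect of a single misclassified patient, not an estimate of the bias. The example durations are likewise illustrative.

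**What to change.** In SAP 4.4.2:

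- Link contiguous entries with the same preferred term into one episode.
- Count the episode as a TEAE only if its first onset is on or after first dose within the existing window, or if a post-dose grade in that window exceeds the last pre-dose grade.
- Replace the SAE start date parenthesis in (i)2 with this grade comparison.
- Keep the provisions for missing onset dates and for late treatment-related SAEs.
- Compute AE and AESI duration from the first start to the last end of the episode, and treat the episode as ongoing if its last entry is ongoing. Carry this into SAP 5.2.11.2.

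The cost is SAP wording and a record-linking step in programming, with medical review of a few links. No new data are needed.
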